Single-use brushing studies are often used as screening tools to give an initial indication of cleaning performance. However, it is not unreasonable to expect toothbrushes that perform well after a single brushing to show greater plaque removal with continued use ([Slot et al. 2012](#)). A longer period of 'home use' allows study subjects to familiarize themselves with a new toothbrush and provides a more representative picture of product performance over time. Longer term toothbrushing studies would also be required to investigate gingival health benefits. In this methodology development study, plaque removal efficacy will be investigated after three separate (on-site) single brushing events (without and with a period of familiarization with the subject's assigned study toothbrush):

- Day 0: first use, no familiarization;
- Day 7: 1 week's familiarization;

Property of GSK Consumer Healthcare - Confidential

May not be used, divulged, published or otherwise disclosed without the consent of GSKCH

SP1963/SOP-208661: Template Version: 14 Mar 2019

- Day 28: 4 weeks' familiarization;

and after an extended period of twice daily brushing (7 and 28 days). The 28 day treatment period has been selected to help inform the design of future longer term studies, while facilitating subject visit scheduling for this study.

Clinical efficacy assessments will be performed at a single clinical site by a single dental examiner to eliminate inter-examiner variability. Intra-examiner variability will be monitored by performing repeat clinical assessments for both plaque indices, in randomly selected subjects, across the study period.

Toothbrush efficacy studies typically include a period of abstinence from oral hygiene prior to clinical assessment visits (i) to standardize oral hygiene practice in the study population and (ii) ensure sufficient plaque growth on the tooth for efficacy evaluation. A systematic review of manual toothbrush studies (59 publications) reported 23–25 hours as the most common period of plaque accumulation prior to brushing efficacy evaluation, 12–18 hours was the next most common ([Slot et al. 2012](#)). In this study, subjects will abstain from toothbrushing for 12–18 hours prior to Visits 2–4 to align with other GSK CH brushing studies.

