12.2 Statistical Methods and Analytical Plan

Additional details of the proposed statistical analysis will be documented in the statistical reporting and analysis plan (RAP), which will be written following finalization of the protocol and prior to study unblinding/analysis (as appropriate).

In this study, baseline is defined as the Day 0 pre-brushing mean plaque score for each index (RPI/TPI). Day 7 and Day 28 pre-brushing plaque levels will also be used to assess plaque removal after single brushing events at these timepoints, noting these values may be influenced by treatment used.

Plaque removal efficacy after first use (change from baseline) will be tested under the null hypothesis:

- H_0 : there is no change from the baseline plaque level;
- H_1 : there is a change from the baseline plaque level.

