12.3.5 Secondary Analyses

Secondary outcome variables include change from baseline in:

- Mean RPI_{overall} (Day 7, Day 28)
- Mean TPI_{overall} (Day 7, Day 28)
- Mean RPI_{gingival margin} (Day 0, Day 7, Day 28)
Sites A, B and C will be used for calculations
- Mean RPI_{inter-proximal} (Day 0, Day 7, Day 28)
Sites D and F will be used for calculations
- Mean TPI_{inter-proximal} (Day 0, Day 7, Day 28)
Mesial and distal sites will be used for calculations

Secondary outcome variables will be derived, based on relevant tooth sites, as the primary outcome variables, with the following summaries generated and analyses performed.

Variable Calculation	Timepoint	Type of Analysis
Actual value	Day 0 (pre- and post-brushing)	Summary statistics

	Day 7 (pre- and post-brushing) Day 28 (pre- and post-brushing)	Plot of pre- and post-brushing values for Days 0, 7 and 30 Box plots
Change from baseline [Day 0 (pre-brushing)]	Day 7 (pre- and post-brushing) Day 28 (pre- and post-brushing)	Summary statistics Plot of change from baseline for Days 7 and 30 ANCOVA for within treatment comparisons

Summary statistics (number of subjects, mean, median, SE, SD, minimum, maximum) will be presented for each outcome variable at each assessment time point by treatment group.

For change from baseline calculations, baseline will be the mean Day 0, pre-brushing plaque score; percent change will also be presented and calculated as $100 \times (\text{Value} - \text{Baseline Value}) / \text{Baseline Value}$. This percent change will be calculated from the aggregated mean levels not at the individual subject level.

Actual mean plaque scores (\pm SE) for both indices will be plotted over time by treatment group. Pre-brushing values will be set at the nominal time recorded (Days 0, 7 and 28); post-brushing values will be set at a small nominal time after (Days 0.5, 7.5 and 28.5). Box plots will also be presented for each outcome variable, over time by treatment group

For variables to be formally analyzed to test for a significant change from zero, change from baseline will be analyzed using an ANCOVA model, with treatment as a fixed effect and the appropriate baseline value as a covariate, as per the primary analysis. For TPI analyses, an extra factor will be included for the RPI_{gingival/interproximal} stratification level (lower/higher). Adjusted mean changes, 95% CIs and p values for change from zero will be presented.

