1.2 Study Objectives

Study objectives and endpoints are defined in [Table 1-2](#):

Table 1-2 Study Objectives and Endpoints

Objectives	Endpoints
Primary	
To evaluate the within-treatment supra-gingival plaque removal efficacy of four manual toothbrushes after a single brushing event (first use).	Change from pre- to post-brushing in mean RPI - overall* (Day 0). Change from pre- to post-brushing in mean TPI - overall (Day 0). * all sites assessed
Secondary	
To evaluate the within-treatment supra-gingival plaque removal efficacy of four manual toothbrushes after single brushing events, following 7 and 28 days familiarization with the brush.	Change from baseline (Day 0 pre-brushing) to post-brushing in mean RPI and mean TPI - overall (Day 7, Day 28). Pre- and post-brushing mean RPI and mean TPI- overall (Day 7, Day 28).
To evaluate the within-treatment supra-gingival plaque removal efficacy of four manual toothbrushes at the gingival margin and from inter-proximal sites, after single brushing events, following 0, 7 and 28 days familiarization with the brush.	Change from baseline (Day 0 pre-brushing) to post-brushing in mean RPI and mean TPI - gingival margin sites (RPI only); inter-proximal sites (Day 0, Day 7, Day 28). Pre- and post-brushing mean RPI and mean TPI - gingival margin sites (RPI only); inter-proximal sites (Day 0, Day 7, Day 28).
To evaluate the within-treatment supra-gingival plaque removal efficacy of four manual toothbrushes after 7 and 28 days twice-daily brushing.	Change from baseline (Day 0 pre-brushing) in mean RPI and mean TPI - overall; gingival margin sites (RPI only); inter-proximal sites (Day 7 pre-brushing, Day 28 pre-brushing).
Safety	
To assess the safety and oral tolerability of the four manual toothbrushes after first use (Day 0) and over 28 days' use.	TEAEs

This clinical methodology development study will be considered successful if a numerical reduction in supra-gingival plaque levels is observed for each toothbrush after first use (Day 0, pre- to post-brushing), for both clinical measures.

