4.5.1 Efficacy (Secondary)

The secondary efficacy endpoints are:

- Mean RPI_{overall} (Day 7 pre- and post-brushing, Day 28 pre- and post-brushing)
- Mean TPI_{overall} (Day 7 pre- and post-brushing, Day 28 pre- and post-brushing)
- Mean RPI_{gingival margin} (Day 0 pre- and post-brushing, Day 7 pre- and post-brushing, Day 28 pre- and post-brushing), defined as mean RPI score for sites A, B and C
- Mean RPI_{inter-proximal} (Day 0 pre- and post-brushing, Day 7 pre- and post-brushing, Day 28 pre- and post-brushing), defined as mean RPI score for sites D and F
- Mean TPI_{inter-proximal} (Day 0 pre- and post-brushing, Day 7 pre- and post-brushing, Day 28 pre- and post-brushing), defined as mean TPI score for mesial and distal sites

Secondary outcome variables will be derived, based on relevant tooth sites, as the primary outcome variables.

Summary statistics (n, missing, mean, SD, SE, median, minimum, maximum) of pre-brushing, post-brushing and change from Day 0 pre-brushing will be presented for each secondary outcome variable at each assessment time point by study product group in the following tables:

- [Table 14.2.2.1.1](#) for mean RPI_{overall}
- [Table 14.2.2.2.1](#) for mean TPI_{overall}
- [Table 14.2.2.3.1](#) for mean RPI_{gingival margin}
- [Table 14.2.2.4.1](#) for mean RPI_{inter-proximal}
- [Table 14.2.2.5.1](#) for mean TPI_{inter-proximal}

Change from baseline of secondary efficacy variables will be analyzed using ANCOVA model with product group as a fixed effect and the appropriate baseline value as a covariate, as defined below:

- For mean RPI_{overall}: baseline mean RPI_{overall}
- For mean TPI_{overall}: baseline mean TPI_{overall} and RPI stratification level (lower/higher)
- For mean RPI_{gingival margin}: baseline mean RPI_{gingival margin}
- For mean RPI_{inter-proximal}: baseline mean RPI_{inter-proximal}
- For mean TPI_{inter-proximal}: baseline mean TPI_{inter-proximal} and RPI stratification level (lower/higher)

Change from Day 0 pre-brushing to each analysis time points (Visit 2 Day 0 post-brushing, Visit 3 Day 7 pre- and post-brushing and Visit 4 Day 28 pre- and post-brushing) will be summarized for each secondary outcome variable by product group (adjusted mean change, percent change from mean baseline, 95% CIs and p-value for change from zero) in the following analysis tables:

- [Table 14.2.2.1.2](#) for mean RPI_{overall}
- [Table 14.2.2.2.2](#) for mean TPI_{overall}

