- [Table 14.2.2.3.2](#) for mean RPI_{gingival margin}
- [Table 14.2.2.4.2](#) for mean RPI_{inter-proximal}
- [Table 14.2.2.5.2](#) for mean TPI_{inter-proximal}

Percent change from mean baseline will be derived as: $100 \times (\text{Adjusted Mean Change} / \text{Mean Baseline Value})$. Adjusted Mean Change will be derived from ANCOVA model.

The assumption of normality and homogeneity of variance in the ANCOVA models will be investigated. Violation of this assumption will be overcome using a suitable data transformation or a non-parametric technique (e.g. Wilcoxon Sign Rank test).

Actual mean plaque scores (\pm SE) for all secondary efficacy endpoints will be plotted over time by study product group for all subjects in mITT population in the following figures:

- [Figure 14.2.2.1.1](#) for mean RPI_{overall}
- [Figure 14.2.2.2.1](#) for mean TPI_{overall}

-
- [Figure 14.2.2.3.1](#) for mean RPI_{gingival margin}
 - [Figure 14.2.2.4.1](#) for mean RPI_{inter-proximal}
 - [Figure 14.2.2.5.1](#) for mean TPI_{inter-proximal}

Pre-brushing values will be set at the nominal time recorded (Days 0, 7 and 28), while post-brushing values will be set at a small nominal time after (Days 0.5, 7.5 and 28.5).

All RPI index data collected in the eCRF will be listed in [Listing 16.2.6.1.2](#) for all randomized subjects while TPI index data collected in the eCRF will be listed in [Listing 16.2.6.2.2](#) for all randomized subjects.

The listings of derived scores of secondary efficacy variables by subject will be presented for all randomized subjects as follows:

- [Listing 16.2.6.1.1](#) for mean RPI_{overall}
- [Listing 16.2.6.2.1](#) for mean TPI_{overall}
- [Listing 16.2.6.1.3](#) for mean RPI_{gingival margin}
- [Listing 16.2.6.1.4](#) for mean RPI_{inter-proximal}
- [Listing 16.2.6.2.3](#) for mean TPI_{inter-proximal}

These listings will include subject number, visit, pre-brushing mean scores, post-brushing mean scores, change from pre-brushing to post-brushing, and change from Day 0 pre-brushing.

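### The same-visit pre- to post-brushing change at Days 7 and 28 is only listed by subject and never contrasted with Day 0, so a change in removal with familiarization has no planned estimate or interval

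*Protocol*

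**What the plan says.** Protocol 4.2 makes familiarization a feature of the design: "plaque removal efficacy will be investigated after three separate (on-site) single brushing events (without and with a period of familiarization". The three events are first use, one week of use and four weeks of use. The same section says of the study's length that "The 28 day treatment period has been selected to help inform the design of future longer term studies".

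The matching secondary objective in SAP 1.2 concerns within-treatment efficacy "after single brushing events, following 7 and 28 days familiarization with the brush". Its endpoints are the change from Day 0 pre-brushing to post-brushing, and the pre- and post-brushing means.

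Protocol 12.2 defines baseline as Day 0 pre-brushing, then adds: "Day 7 and Day 28 pre-brushing plaque levels will also be used to assess plaque removal after single brushing events at these timepoints". It notes that these values may be influenced by treatment.

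The analysis is described in three places:

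- Protocol 12.3.5 assigns "ANCOVA for within treatment comparisons" to change from Day 0 pre-brushing.
- SAP 4.5.1 uses an "ANCOVA model with product group as a fixed effect and the appropriate baseline value as a covariate", with the RPI stratum added for TPI. The results tabulated are "Change from Day 0 pre-brushing to each analysis time points (Visit 2 Day 0 post-brushing, Visit 3 Day 7 pre- and post-brushing" and the same pair at Day 28, each with a 95% CI and a p-value for change from zero.
- The same-visit change at Days 7 and 28 appears in the by-subject listings of SAP 4.4.1.1 and 4.5.1, whose contents include "change from pre-brushing to post-brushing, and change from Day 0 pre-brushing".

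**The concern.** At Day 0 the planned endpoint is single-brushing removal, because baseline is that day's own pre-brushing score. At Days 7 and 28 it is not. The post-brushing score is still compared with Day 0 pre-brushing, so the result combines the plaque reduction already present when the subject arrives with the plaque removed on the day.

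A reader who sees a larger reduction at Day 7 than at Day 0 may conclude that familiarization improves brushing, when single-event removal may be unchanged or lower. The study is meant to inform the design of later toothbrush studies. Whether a period of home use changes what a single brushing removes is one thing these data could help settle, and the data are already being collected.

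**Working it through.** The plan gives no power, SD or correlation for this contrast, and Protocol 12.1 states that no formal sample size was produced. There is therefore no planned figure to reproduce. The check has three parts.

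**1. What the planned result contains.** Write Pre and Post for mean scores, with the day as index, and removal R = Pre − Post at the same visit. Then

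Pre0 − Post7 = (Pre0 − Pre7) + R7.

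The left side is the planned Day 7 post-brushing reduction. The first term on the right is carry-over from home use; the second is removal on the day. The familiarization contrast is R7 − R0, and Day 28 works the same way.

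Illustration with assumed mean scores, Day 0 going from 0.70 to 0.40 (planned change −0.30, R0 = 0.30):

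| Day 7 pre → post | Planned change (Post7 − Pre0) | R7 | R7 − R0 |
|---|---|---|---|
| 0.60 → 0.30 | −0.40 | 0.30 | 0.00 |
| 0.60 → 0.36 | −0.34 | 0.24 | −0.06 |
| 0.70 → 0.30 | −0.40 | 0.40 | +0.10 |

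Rows 1 and 3 give the same planned result but different contrasts. In row 2 the planned result looks 0.04 better than Day 0 although removal fell by 0.06.

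**2. What can be recovered from the planned tables.** Subtracting the Day 7 pre-brushing adjusted change from the Day 7 post-brushing one gives −R7 as a point value, exactly so only if the same subjects contribute to both. Comparing it with Day 0 gives a point difference under the same condition. Its standard error cannot be derived: it needs the covariance between time points within subject, which separate ANCOVAs do not report. No model in the SAP text has a visit, visit-by-product or subject term. SAP 4.4.1.3 lists no supportive analyses, and SAP Table 5-1 adds no such contrast.

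**3. The precision an added contrast would have.** Inputs: 20 subjects per brush and 80 in total (Protocol 12.1), all assessed at both visits (assumed); equal SD of removal at both visits (assumed); within-subject correlation ρ from 0.3 to 0.7 (assumed).

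- SD of the difference: SD_D = SD × √(2(1 − ρ)), which is 1.183, 1.000 and 0.775 SD at ρ = 0.3, 0.5 and 0.7.
- 95% half-width: t × SD_D / √n.
- Per brush: 2.093 / √20 = 0.468, times SD_D.
- Over 80 subjects: 0.223 times SD_D.

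| ρ | Per brush, n = 20 | Over brushes, n = 80 |
|---|---|---|
| 0.3 | 0.55 SD | 0.26 SD |
| 0.5 | 0.47 SD | 0.22 SD |
| 0.7 | 0.36 SD | 0.17 SD |

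The estimate is coarse for one brush and reasonably informative over all four.

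**The case against.** The strongest reply is that the study delivers what its objectives ask. Every efficacy objective is within-treatment, none asks for removal to be compared between visits, and the success criterion rests on Day 0 alone (Protocol 3, SAP 1.2). The secondary endpoints are themselves defined from Day 0 pre-brushing, and pre- and post-brushing means are tabulated and plotted for all three visits. This stands, and it limits the point to a missed analysis.

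Two stronger readings are tempting, and the documents do not support them:

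- *No analysis compares one visit with another.* SAP 4.5.1 formally compares the Day 7 and Day 28 scores with Day 0 pre-brushing. What is missing is a comparison of same-visit removal.
- *Visits 3 and 4 exist mainly to test familiarization.* They also serve the objective on 7 and 28 days of twice-daily brushing, and 28-day safety. Protocol 4.2 gives visit scheduling as a further reason for the 28 days.

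A second reply is that the contrast would be weak evidence. No arm has its first use at Day 7 or Day 28, so the comparison is uncontrolled, and examiner drift or visit effects cannot be separated from familiarization. Subjects enter on a Day 0 pre-brushing gingival/interproximal RPI of at least 0.6. Regression to the mean can then lower later pre-brushing scores and make first-use removal look relatively large. This also stands. It is a reason to label the contrast, not to omit it.

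A third reply is that comparing visit-specific intervals by eye is conservative: with positive correlation, treating visits as independent makes the SE of a difference too large by 1/√(1 − ρ), that is 1.20, 1.41 and 1.83 times at ρ = 0.3, 0.5 and 0.7. That is correct for intervals on same-visit removal. The planned intervals at Days 7 and 28 describe a different quantity, so they do not offer even that comparison.

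**Conclusion.** The point holds in a limited form. The SAP text plans no estimate, interval or test of whether single-brushing removal at Day 7 or Day 28 differs from Day 0. It analyses same-visit removal at those visits nowhere, although Protocol 12.2 says the pre-brushing levels will be used for that assessment. The planned post-brushing results can point the wrong way on single-event removal. A point difference can be worked out roughly from the means, without a standard error.

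The primary analysis is unaffected, and it should not be inferred that a stated objective is unanswered. The size is what an added contrast would offer: a half-width of about 0.47 SD per brush (0.55 to 0.36 for correlations of 0.3 to 0.7) and 0.22 SD over 80 subjects. This rests on assumed correlations, equal SDs and full attendance; the plan makes no allowance for dropout. The list of data displays (SAP Attachment 1) is not reproduced in the document, so the conclusion rests on the SAP's text.

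**What to change.** Add to SAP 4.5.1, for each index, an exploratory repeated-measures model of same-visit removal (pre minus post) at Days 0, 7 and 28, with brush, visit, brush-by-visit and an unstructured within-subject covariance. Report, with 95% CIs, per brush and averaged over brushes:

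- same-visit removal at each visit;
- Day 7 minus Day 0 and Day 28 minus Day 0.

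State beside the results that the contrasts are uncontrolled before-after comparisons, open to regression to the mean from the entry rule and to examiner or visit effects. A version adjusted for that visit's pre-brushing score is reasonable because removal depends on the plaque available. It should be a sensitivity analysis only, since Protocol 12.2 itself warns that treatment may influence those scores. Record the addition in SAP Table 5-1.

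The cost is one SAP paragraph and two tables. No new data are needed, and the same-visit change is already derived for the listings. The one real downside is that the contrast could be over-read as a causal effect of familiarization, which the labelling is there to prevent.

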4.3 Justification for Dose

The study products are manual toothbrushes, intended for topical oral use. Subjects will be provided with a regular fluoride toothpaste to use with the lead-in toothbrush and with their assigned study toothbrush for the duration of the study.

The usage regimen of twice daily brushing (morning and evening) will be the same for all subjects and is based on widely recommended oral hygiene practice/typical consumer habit. Study subjects will be required to brush for 1 timed minute with their assigned study toothbrush and the regular fluoride toothpaste provided (according to their normal habit) on each brushing occasion, for 28 days (\pm 2 days). Study toothbrushes will be evaluated under normal use conditions; no professional oral hygiene instruction will be given.

Eligible subjects will complete a supervised brushing with the lead-in toothbrush and the regular fluoride toothpaste provided at the end of the Screening visit (while still at the study site) to enable staff to confirm correct usage and encourage compliance with the required brushing regimen throughout the study.

4.4 End of Study Definition

A subject is considered to have completed the study if they completed all phases of the study, including the last visit or the last scheduled procedure shown in the Schedule of Activities.

The end of this study is defined as the date of the last scheduled procedure shown in the Schedule of Activities for the last subject in the trial

5 STUDY POPULATION

5.1 Type and Planned Number of Subjects

The study will be conducted in male and female subjects in good general and oral health. Sufficient subjects will be screened (approximately 200 subjects) to enter approximately 100 subjects into the lead-in period and so ensure approximately 80 subjects are randomized to study treatment. Subjects will be recruited by the clinical site.

Subjects may be recruited via letters advertising the study, sent with routine appointment letters from the hospital and/or local general dental practices; via advertisements placed around university and hospital sites, and in local general dentist practices; by advertisements included in university newsletters and e-mails sent to university staff and students; or by word of mouth. Students of, and staff employed by, the investigational site will not be recruited.

An enrolled subject is one who has agreed to participate in the clinical study following completion of the informed consent process and has successfully met eligibility criteria to proceed beyond the screening visit, as applicable for the protocol design.

This study can fulfill its objectives only if appropriate subjects are enrolled. The following eligibility criteria are designed to select subjects for whom participation in the study is considered appropriate. All relevant medical and non-medical conditions should be taken into consideration when deciding whether a subject is suitable for this protocol.

Subject eligibility to participate in the clinical study should be reviewed and documented by an appropriate member of the investigator's study team before subjects are included in the study.

